6.4 Ethical Considerations

Using the informed consent forms, the study will be explained to all participants and written informed consent (Appendices 13 - 15) will be obtained from respondents for participating in the study. Informed consent for audio recordings will be obtained as part of the main informed consent form based on the Malawi ethics board requirements. Permission was obtained from the Lilongwe District Health Officer (appendix 16) to conduct the study at the STI and VMMC clinics. All data forms, informed consent forms, interview notes and voice recorders will be stored under a double-lock system at the UNC Project during the study period. Electronic data

will be stored in a password-protected database. Both paper and electronic data will not contain identifiable information. Ethics approvals have been obtained from the National Health Sciences Research Ethics committee of Malawi (NHRSC) (appendix 17) and the University of North Carolina at Chapel Hill Internal Review Board (appendix 18). Final ethics approval will be obtained from the University of the Witwatersrand Human Research Ethics Committee (HREC)

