4 DEFINITIONS

Acceptability: the perception among men and healthcare workers that the adaptable RITE intervention is agreeable, palatable and satisfactory.

Appropriateness: the perceived fit of the adaptable RITE intervention to address the problem of low uptake of VMMC among men and healthcare workers.

Clinic escort: the act of escorting/accompanying a participant interested in VMMC from the STI clinic to the VMMC clinic to ensure linkage to care.

Contamination: a situation where the study population become exposed to more than one intervention component

Feasibility: the extent to which the adaptable RITE intervention will be successfully carried out at Bwaila STI clinic.

Intensified health education: consistent and setting-specific education on VMMC incorporated into the routine STI/HIV health education provided at Bwaila STI clinic.

Interference: a scenario where other stakeholders implement an intervention(s) aimed to scale-up the uptake of VMMC at the study sites which may affect attribution.

Seasonality: periodic variation in the uptake of VMMC with calendar time

SMS reminder tracing: the act of reminding participants with a VMMC appointment about their date of procedure through short messaging service.

Time-to-uptake: the number of days from the day a participant is offered VMMC to the day they undergo VMMC

Transport reimbursement: refunding money used for transportation to Bwaila district hospital for participants who undergo VMMC using standard Malawi government rates.

Uptake: the action of undergoing VMMC.

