6.2 Study setting

The study setting is the Bwaila STI Clinic (BSC) and Bwaila VMMC clinic at Bwaila District Hospital (BDH). BDH is a public secondary level facility in Lilongwe and the only facility offering specialized STI care situated in a busy central town area of the Lilongwe district. Approximately 80 patients visit BSC per day. The VMMC clinic and BSC are about 300 meters apart within the BDH campus. Twenty (20) people comprising nurses, clinicians, HIV testing services (HTS) counsellors, receptionists and support staff run BSC. As standard of care, all STI patients at BSC receive group health education (GHE) and are offered opt-out provider initiated HIV testing as standard of care, before receiving care for their STIs. We propose to integrate intensified health education to the GHE. About two to three GHE sessions are conducted per day with different cohorts of patients based on their time of arrival at the clinic however only one GHE includes education on VMMC. The clinic receptionist assisted by a nurse or counsellor conducts GHE. The first GHE session includes a mobilizer from the VMMC clinic who conducts an educational talk on VMMC every morning at the STI clinic and refers men to the VMMC clinic using referral slips. The additional GHE sessions do not have educational talks by the mobilizer. We will train the clinic receptionist, counselors, nurses and the mobilizer to conduct intensified health education. As standard of care, uncircumcised men with STIs are supposed to be offered VMMC at the STI clinic by clinicians however this is not reinforced. Data on demographics, HIV testing and treatment, sexual history and STIs are collected routinely through an electronic medical registry.

The VMMC clinic has a director, administrator, program officers, clinicians (male and female), nurses (both male and female), data clerks, mobilizers and support staff. A team consisting of one clinician, an assisting nurse and other support staff conduct circumcisions. Circumcisions are

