done at the VMMC clinic and in the community through outreach clinics and mobile vans. Data such as demographics, referral source, date and outcome of VMMC are recorded in registers. We will use these registers to track men referred from the STI clinic who will undergo circumcision. Men attending the STI clinic may either be index cases (symptomatic) or sexual partners (symptomatic or asymptomatic). Men with symptomatic STIs will not undergo VMMC on the same day of their STI clinic visit until they complete treatment for their current STI.

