6.2 Data Collection

Overall, we will collect demographic characteristics for our study population. Among men accessing STI care, we will collect demographic data such as age, marital status, educational status and socioeconomic status. Additional data collected may include sexual history, HIV and ART status. Data will be collected using the routine electronic medical registry at Bwaila STI clinic and exported into a Microsoft Excel spreadsheet.

Objective 1: To compare uptake of voluntary medical male circumcision between the standard of care and the different combinations of the RITE intervention among men attending Bwaila STI clinic in Lilongwe Malawi

Uptake in this study will be the action of undergoing VMMC. Uptake of the intervention will be measured for each implementation block. Data on demographic characteristics including contact information, HIV history, sexual history and STI data will be collected for all participants from

the STI clinic using a routine clinical form through the electronic medical registry (EMR) (Appendix 2). We will collect data on the number of uncircumcised men offered VMMC and the number of men referred to the VMMC clinic from the STI clinic using study specific data collection form (Appendix 3). In addition the number of men who underwent VMMC will be collected from routine VMMC clinic registers using a study specific data collection form (Appendix 4). Data clerks and the VMMC mobilizer will collect these data on a daily basis from both clinics. SMS tracing attempts will be collected separately on a study-specific SMS tracing form (Appendix 5). The content of the SMS will be designed during the pre-test but we have included a draft of what the content may include (Appendix 5). The data will be collected and collated daily by a data clerk. Data will be entered into a Microsoft Excel spreadsheet by a data assistant.

Objective 1a: To compare time-to-uptake of voluntary medical male circumcision between the pre- and post-intervention periods among men attending Bwaila STI clinic in Lilongwe Malawi

Time-to-uptake will be the number of days from the day a participant is offered VMMC to the day they undergo VMMC. Data clerks will collect data on the date the participant is offered VMMC from the STI clinic using a study-specific data collection form (Appendix 3) while the date the participant undergoes VMMC will be collected from routine VMMC clinic registers on a daily basis and entered into Microsoft Excel.

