Uptake will be calculated as a proportion - the number of men who will undergo VMMC divided by the number of uncircumcised men offered VMMC at the STI clinic. Uptake will be calculated for each implementation block. Uptake for each block will be compared against SOC using Student's T-test at $\alpha=0.05$ significance level and 95% confidence interval, assuming normal distribution.

Objective 1a: To compare time-to-uptake of voluntary medical male circumcision between the standard of care and intervention period among men attending Bwaila STI clinic in Lilongwe Malawi

Time-to-uptake of VMMC will be calculated as the number of days taken for an individual to undergo circumcision at the VMMC clinic from the day they were offered circumcision at the STI clinic. To compare time-to-uptake between SOC and the intervention blocks, we will conduct time-to-event analysis to estimate duration to circumcision and Kaplan Meier curves will be plotted and compared between SOC and implementation blocks. We will also study factors affecting time-to-uptake using cox regression.

Objective 1b: To assess factors affecting uptake of voluntary medical male circumcision among men attending Bwaila STI clinic in Lilongwe Malawi

We will assess factors affecting uptake of VMMC using logistic regression modeling. We will use univariate models to assess association. Covariates with $P<0.05$ and those based on expert knowledge of this topic will be fit into multivariate logistic regression models to control for confounders.

Objective 2: To develop STI clinic setting-specific voluntary medical male circumcision educational material at Bwaila STI clinic in Lilongwe Malawi

We will use thematic analysis approach for qualitative analysis of the consultative meeting notes. The notes will be coded and salient themes will be identified. The content and delivery methods will be deduced from the salient themes.

Objective 3: To assess the acceptability, appropriateness and feasibility of the adaptable RITE intervention among men and healthcare workers at Bwaila STI clinic in Lilongwe, Malawi.

We will use mixed methods to assess acceptability, appropriateness and feasibility. For acceptability, appropriateness and feasibility quantitative surveys, these outcomes will be

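### The no-identifiers statement conflicts with the contact data and record linkage that the outcomes need, and circumcisions may be traced more completely in blocks two to four than under standard of care

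*Combined protocol and SAP*

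**What the plan says.** Section 6.4 Ethical Considerations describes locked storage of forms and recorders and a password-protected database, then says: "Both paper and electronic data will not contain identifiable information". It names no exception, key file or de-identification step.

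Section 6.2 Data Collection, Objective 1, says: "Data on demographic characteristics including contact information, HIV history, sexual history and STI data will be collected for all participants". The route is the STI clinic's electronic registry. It adds: "SMS tracing attempts will be collected separately on a study-specific SMS tracing form".

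Uptake is defined under Data Analysis in section 6.3 as "the number of men who will undergo VMMC divided by the number of uncircumcised men offered VMMC at the STI clinic". Time-to-uptake is defined in section 4 as "the number of days from the day a participant is offered VMMC to the day they undergo VMMC". Procedures and their dates come from the VMMC clinic registers, which also hold demographics and a referral source. Section 6.2 Study setting gives their use: "We will use these registers to track men referred from the STI clinic who will undergo circumcision".

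The aids to tracing a man differ by period:

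- **SOC** (6.2 Study setting): a mobilizer attends the first education session of the day and "refers men to the VMMC clinic using referral slips". Later sessions have no mobilizer talk, and offers by clinicians are expected but not enforced.
- **Block one** (6.6.2): education only.
- **Blocks two to four** (6.6.1, 6.6.2): interested men are walked to the VMMC clinic by escorts, who are data clerks and clinic aides.
- **Block four**: men not circumcised the same day carry a coupon, and the procedure is confirmed in the register before payment.

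**The concern.** There are two linked problems.

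The first is a conflict of text. Contact details are collected alongside HIV and sexual history, and SMS reminders need a phone number, yet section 6.4 says without qualification that nothing identifiable is held. The analyses also depend on joining two clinics' records man by man, and the text shown does not say by what key.

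The second is a risk to the primary comparison. If circumcisions are found by looking for men marked as referred, a man who was offered VMMC under SOC, received no slip and walked over on his own could be entered under another source and counted as not circumcised. An escorted man, or one presenting a coupon, is less likely to be missed. Any such gap would favour the intervention. It would also affect time-to-uptake, because a missed procedure would be treated as an event that had not happened. Section 6.5 Limitations does not mention it.

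**Working it through.** **1. Does the analysis need person-level linkage?**

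- Time-to-uptake subtracts an offer date recorded at the STI clinic from a procedure date recorded at the VMMC clinic, for the same man.
- The logistic and Cox models join registry covariates to that man's outcome.
- Uptake by block needs the link as well. Men with symptomatic STIs are deferred until treatment is complete, and blocks are separated by only one week, so a procedure can fall after the block in which the offer was made. A register count by date would not assign it correctly.

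All three need a key. A study number could serve, but the text shown does not describe one.

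**2. Do the tracked group and the denominator agree?** The Study setting section tracks referred men. The denominator is men offered VMMC. Data Collection counts offered and referred men separately, so the plan itself treats them as different groups.

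**3. The plan's own counts.** Section 6.3 gives 27 men per day and 28% circumcised. 27 × 0.72 = 19.4, taken as 19. 19 × 20 clinic days = 380 per month, and 380 × 6 = 2280, which matches the stated figure. Nothing here disputes it. At 3 to 4 weeks per block and 5 clinic days per week (assumed), a block holds 19 × 15 = 285 to 19 × 20 = 380 men. The length of the SOC period is not stated; the same size is assumed.

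**4. What would unequal capture do?** Let true uptake p be the same in both periods, and let c be the fraction of circumcisions found. Observed uptake is p × c, so with no true effect

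observed ratio = c(RITE) / c(SOC).

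The documents give neither p nor c. All capture rates below, and p of 10% or 20%, are assumptions. For example, with 380 men and p = 10% there are 38 circumcisions in each period. At 80% capture 30.4 are recorded, and at 95% capture 36.1.

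The chance of a significant result favouring RITE uses the normal approximation for two proportions, two-sided α = 0.05 (section 6.3 gives 0.05 without stating sidedness). Worked case, 380 men per period, p = 10%, capture 70% against 95%:

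- Observed proportions: 0.070 and 0.095; difference 0.025; pooled 0.0825.
- SE under the null = √(2 × 0.0825 × 0.9175 / 380) = 0.01996.
- SE under the alternative = √((0.070 × 0.930 + 0.095 × 0.905) / 380) = 0.01994.
- Chance = Φ((0.025 − 1.96 × 0.01996) / 0.01994) = Φ(−0.71) = 24%.

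| SOC capture | RITE capture | Spurious ratio | 285 men, p = 10% | 380 men, p = 10% | 380 men, p = 20% |
|---|---|---|---|---|---|
| 90% | 95% | 1.06 | 4% | 4% | 5% |
| 80% | 95% | 1.19 | 9% | 11% | 19% |
| 70% | 95% | 1.36 | 19% | 24% | 46% |

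With equal capture the chance in this direction is 2.5%.

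**The case against.** The strongest reply is that the bias is hypothetical. No section makes the referral label the only matching key: the register also holds demographics, and data clerks record each offer date on a study form and read the register daily. The stated numerator is simply men who undergo VMMC. Appendices 2 to 5, the data forms, are listed but not shown and may carry an identifier or a matching rule. Section 6.4 may also mean only that research files are de-identified while contact details stay in the routine registry.

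Much of this stands, and it rules out several stronger readings that a reader might infer:

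- **That RITE uptake is in fact better captured, and increasingly so with each component.** Block one adds no tracing aid. SMS reminders are not described as touching the register. Escorts act at the STI visit, with none described for a deferred man's return. The block-four register check is a payment control.
- **That section 6.4 makes linkage impossible.** Coded records can be linked without names.
- **That participants are told something untrue.** The consent forms are not shown.

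The objection does not remove the conflict of text, since section 6.4 covers paper and electronic data without exception. Nor does it supply a matching rule, or explain why referred men are tracked when offered men are counted.

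**Conclusion.** The conflict between section 6.4 and section 6.2 Data Collection is plain on the text and must be reconciled. Differential capture is a plausible risk and not a demonstrated bias: circumcisions may be found more completely in blocks two to four than under SOC or block one.

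Its size cannot be computed from the documents. Under the assumed rates it runs from minor (90% against 95%: ratio 1.06) to serious (70% against 95%: ratio 1.36, with a 24% to 46% chance of a false finding at 380 men per period and true uptake of 10% to 20%). Nothing in the documents points to one end of that range. The point is still worth acting on, because the remedy is cheap and linkage data not recorded during SOC may not be recoverable later.

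**What to change.** - From the first SOC day, give every man offered VMMC a study number, recorded on the offer form and on his referral slip.
- Match all offered men to all VMMC register entries by one written rule, the same in SOC and every block, whatever referral source is recorded.
- Define the uptake numerator as matched men, attributed to the period of their offer, and report match completeness by block.
- Reword section 6.4 to say that identifiers are held separately and securely for linkage and SMS, and that analysis files carry only the study number. Check that the participant information agrees.
- Add differential outcome capture to section 6.5.

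I would not ask for blinded matching: blocks are calendar periods, so register dates reveal them, and data clerks also act as escorts.

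The cost is protocol wording, a number on an existing slip and some clerk time. The downside is a linkage list that must be protected and shown to the ethics committees. Section 6.4 says one ethics approval is still to come, so the correction can go in with that submission.

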6.5 Limitations and anticipated challenges

Contamination may be challenge in this implementation study however, we believe we have partly addressed this by using wash-out periods of one week between interventions. Selection bias may be a potential limitation if men with certain common characteristics enroll to a specific intervention block and affect the uptake of VMMC. Seasonality (circular trends) is a well-known confounding factor in VMMC research. Men in LMICs prefer to undergo circumcision in the cold season [39]. Our study will recruit participants during a period that will transition through the cold season however, we will monitor circular trends by measuring the prevalence of circumcision among men at Bwaila STI clinic. Interference in this study will be defined as a stakeholder implementing any intervention aimed to scale-up the uptake of VMMC at the study sites.

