Clinic escorts will be the act of escorting/accompanying a participant interested in VMMC from the STI clinic to the VMMC clinic to ensure linkage to care. We propose to use clinic escorts who will accompany men interested in VMMC from the STI clinic to the VMMC clinic to ensure that men are not lost in transit. Men may either undergo same day VMMC (if asymptomatic) or have an appointment for VMMC on a later date if symptomatic or if they have other viable reasons. Escorting patients is beneficial in linkage and retention in care and is policy in varied clinical settings [32]. Clinic escorts will be data clerks and clinic aides.

SMS Tracing (T)

SMS reminder tracing will be the act of reminding participants with a VMMC appointment about their date of procedure through short messaging service. This PhD study proposes to use SMS tracing to remind men who could not have same day VMMC of their appointment for VMMC. The content and frequency of the SMS messages will be guided by the findings from formative research however we have included a modifiable guide of the messages. Cell phone tracing is also a proven strategy for minimizing loss to follow-up and improving retention [33–35]

Transport Reimbursement (R)

Transport reimbursement will be refunding money used for transportation to the Bwaila district hospital for participants who undergo VMMC using standard Malawi government rates.

Transport reimbursement equivalent to US\$10 as stipulated by the National Health Sciences Research Ethics Committee (NHSRC) in Malawi, will be offered to all men who will undergo VMMC on the day of the procedure to minimize the opportunity cost. Incentives also have been shown to improve many medical outcomes [40, 41]. Eligible men will receive transport reimbursement when they undergo VMMC. Men who cannot have same day circumcision will receive a coupon to present on the day of the procedure for reimbursement. Documentation of the VMMC procedure will be confirmed in the VMMC clinic's procedures register before payment.

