This will be full roll-out of our intervention. The intervention will have four implementation blocks (Appendix 1) that will be different combinations of the intervention components in an incremental manner. There will be one week of no intervention between interventions as a wash-out period. The implementation will be as follows: First we will observe the SOC VMMC referral process. In **block one**, we will introduce IHE which will then be maintained throughout the implementation period. Clinic escorts combined with IHE in **block two**. **Block three**, IHE, clinic escorts and SMS tracing will be combined. In **block four**, all intervention components will be combined including transport reimbursement to form the full intervention. Supportive supervision and constructive feedback will be maintained throughout the implementation period. Based on the sample sizes detailed below, we anticipate that each intervention block will last about 3-4 weeks.

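### The one-week gap separates blocks only for men circumcised within 7 days of the offer, so SMS reminders can carry over into block two's uptake; the payment rule for block three is ambiguous

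*Combined protocol and SAP*

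**What the plan says.** Section 4 (Definitions) treats contamination as exposure to more than one intervention component. The only safeguard is in section 6.6.2 (Implementation): "There will be one week of no intervention between interventions as a wash-out period". Section 6.5 (Limitations and anticipated challenges) relies on it: "we believe we have partly addressed this by using wash-out periods of one week between interventions". On duration, section 6.6.2 says "we anticipate that each intervention block will last about 3-4 weeks". SMS enters in block three and transport reimbursement in block four.

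Many men cannot be circumcised at the visit. Section 6.2 (Study setting): "Men with symptomatic STIs will not undergo VMMC on the same day of their STI clinic visit until they complete treatment". Under section 6.6.1 (Composition), men may also "have an appointment for VMMC on a later date if symptomatic or if they have other viable reasons". No maximum delay is given.

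Section 6.6.1 defines the two late components by what happens after the visit. For SMS: "SMS reminder tracing will be the act of reminding participants with a VMMC appointment about their date of procedure". Payment "will be offered to all men who will undergo" VMMC, on the day of the procedure. The paragraph goes on to speak of eligible men, and of a coupon given to men who cannot be circumcised the same day.

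The Data Analysis text (within section 6.3, Sample Size Calculation and Justification) defines uptake per block as men circumcised over uncircumcised men offered VMMC, and compares each block with standard of care (SOC). It gives no follow-up window and does not say whether a procedure belongs to the block of the offer or of the procedure.

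**The concern.** The gap separates block periods. Education and escorts act at the STI clinic visit, so for them that is enough. SMS and payment act between the offer and the procedure. A man offered VMMC late in one block and deferred by more than a week can reach his procedure in the next block, when a component that was not part of his own block is running. The only relevant exclusion, in section 6.5 (Exclusion criteria), concerns repeat STI visits; it does not cover a return to the VMMC clinic for the procedure.

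The stepped design is meant to show what each combination of components achieves. If some block-two men receive SMS, block two no longer measures education plus escorts alone, and late events on its time-to-uptake curve occur under block three's components.

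**Working it through.** **Inputs from the documents.** Gap: 7 days. Block length L: 21 or 28 days. Deferral: until treatment is complete, or for other reasons, with no length stated. The plan gives no figure for carry-over, so there is none to reproduce.

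**Assumptions.** Offers are spread evenly over the block, and no man offered VMMC in the gap week is counted. The delay d is varied over a range.

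**Fixed delay.** A man offered on day t has his procedure on day t + d. The next block starts on day L + 7. The share past the gap is the share with t > L + 7 − d, which is (d − 7)/L, held between 0 and 1.

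| Delay | L = 21 | L = 28 |
|---|---|---|
| 7 days or less | 0% | 0% |
| 10 days | 3/21 = 14% | 3/28 = 11% |
| 14 days | 7/21 = 33% | 7/28 = 25% |
| 21 days | 14/21 = 67% | 14/28 = 50% |

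**Exponential delay with mean m.** The share is e^(−7/m) × (m/L) × (1 − e^(−L/m)).

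- m = 7: 0.368 × 0.333 × 0.950 = 12% (L = 21); 0.368 × 0.250 × 0.982 = 9% (L = 28).
- m = 14: 31% and 26%.

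These shares apply to deferred men who are eventually circumcised, not to the whole block. They count calendar overlap, which is an upper limit on exposure: a man whose date falls on the first day of block three may receive no message.

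**What this could do to an uptake figure.** With deferred share D, carried-over share c and SMS effect Δ, block two's uptake by offer date shifts by at most D × c × Δ. Taking D = 0.8 and Δ = 10 percentage points, both purely for illustration:

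- Fixed 2-week delay: 0.8 × 0.333 × 10 = 2.7 points (L = 21) or 0.8 × 0.25 × 10 = 2.0 points (L = 28).
- Exponential delay, mean 7 days: 0.8 × 0.117 × 10 = 0.9 points or 0.8 × 0.090 × 10 = 0.7 points.

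**How far it can travel.** A block-one man meets SMS only if his delay exceeds 7 + L + 7 = 35 or 42 days. An SOC man must wait through blocks one and two and the gap after each: more than 2L + 14 = 56 or 70 days. Block-four men already have every component.

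**Attribution.** Counted by offer date, an effective SMS raises block two. Counted by procedure date, a block-two man circumcised during block three leaves block two's numerator and enters block three's, although he was offered VMMC in block two. The text permits either.

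**The case against.** **The limitation is disclosed.** Section 6.5 claims only that contamination is partly addressed. True, but the plan neither measures what remains nor handles it in the analysis.

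**Early uptake.** Section 5.2 (Problem statement) hypothesizes higher uptake in the first seven days, when the gap would suffice. This could make carry-over small. It is a hypothesis, however; the same section says this interval is not well studied, and higher early uptake still allows later uptake.

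**The SMS list may be restricted in practice.** The SMS and uptake forms (Appendices 5 and 3) are not in the file, and SMS frequency is left to formative work. This stands: the claim is that no visible text sets the restriction. For the same reason it cannot be said that a block-three man loses his reminder in the gap week, only that the plan does not say he keeps it.

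**Payment.** A reader might infer that block-three men deferred into block four are paid as the protocol is written, so that block three partly measures reimbursement. The documents do not support that. The sentence about all men stands beside those on eligible men and coupons, and a man deferred in block three would not normally hold a coupon. A payment made on the day also changes uptake only if he knew of it beforehand, which the documents do not address.

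**Planned comparisons.** Each block is tested against SOC; no test between adjacent blocks is planned. This also stands and limits the damage.

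**Conclusion.** The point holds in a limited form, with medium confidence. A 7-day gap cannot by itself keep SMS from men offered VMMC in block two whose procedure is deferred by more than a week. Payment reaching block-three men is a second, ambiguous route. Both can bias the comparisons of blocks two and three with SOC, and their time-to-uptake curves.

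The size rests on a delay that the documents do not give: no carry-over at 7 days or less, and a quarter to a third of deferred and eventually circumcised men at 2 weeks. If men offered VMMC in the gap week are counted, which the text does not rule out, the protection is weaker.

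Two stronger readings should be resisted. Carry-over is possible, not shown, and its direction depends on an attribution rule that the plan leaves open. Nor does it undermine the main contrast: SOC precedes SMS by two blocks and no component is added after block four, so full RITE versus SOC is largely unaffected.

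**What to change.** 1. Count every VMMC in the block of first offer, within one fixed follow-up window that is the same for SOC and all blocks. Set its length before the data are examined.
2. Restrict the SMS list to men first offered VMMC in blocks three and four, and continue their reminders through the gap week.
3. Reconcile the payment sentences in section 6.6.1 so that eligibility by block of offer is explicit.
4. Record and report how many men received a component outside their block. Add a sensitivity analysis that censors time-to-uptake at the start of the next block.

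The cost is protocol wording and a block code on the SMS list and coupons, which staff must check. Register review must continue after block four until the window closes for the last man offered. The censored analysis will have fewer events. Items 2 and 3 should be settled before block two opens, because exposure given outside a man's block cannot be removed in the analysis.
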